#### **1.2.4 Overview of Clinical Safety of Pacritinib**

Approximately 1128 patients have received pacritinib in 16 completed studies, including 713 patients with myelofibrosis who were assigned to a pacritinib arm. Completed studies include two controlled studies in myelofibrosis (PERSIST-1 and PERSIST-2), five uncontrolled clinical studies in patients with cancer (including the PAC203 Phase 2 dose finding study in patients with myelofibrosis), and nine clinical pharmacology/PK studies.

Among the patients with myelofibrosis treated with pacritinib in the completed controlled and uncontrolled studies, the most commonly (> 10% of all patients) reported treatment-emergent adverse events (TEAEs) related to study drug, by preferred term (PT), were in the system organ class of gastrointestinal (GI) disorders, including diarrhea (56%), nausea (34%), and vomiting (20%), and the System Organ Class of blood and lymphatic system disorders, including thrombocytopenia (25%) and anemia (25%). Although GI-related events were common, they were generally reversible, were of low grade, and rarely led to treatment discontinuation.

#### ***Overview of the PAC203 Phase 2 Dose-Finding Study in Patients with Myelofibrosis***

PAC203 was a dose-finding study in patients with advanced myelofibrosis who experienced intolerance or treatment failure with ruxolitinib. Compared to the PERSIST studies, PAC203 included additional eligibility and monitoring guidelines to mitigate the risk of cardiac and bleeding events. Enrollment was not restricted based on platelet count. The primary objective of the study was to determine the optimal dosage of pacritinib, spanning the dose-response curve

for safety and efficacy established in previous phase 1/2 clinical studies and the phase 3 PERSIST-1 and PERSIST-2 studies. Patients were randomized 1:1:1 to pacritinib 200 mg BID, pacritinib 100 mg BID, or pacritinib 100 mg QD. Of the 161 patients who were randomized and who received treatment, median platelet count was 55,000/ $\mu$ L, and hemoglobin was < 10 g/dL in 70.8% of patients (n = 114). Median duration of treatment was 23 weeks (100 mg QD), 20 weeks (100 mg BID), and 21 weeks (200 mg BID).

At Week 24, the spleen volume reduction response rate ( $\geq$ 35% reduction) was highest in the 200 mg BID arm (9.3%) compared to lower dose arms (100 mg QD: 0% and 100 mg BID: 1.8%). The TSS response rate ( $\geq$ 50% reduction) was similar across all arms (100 mg QD: 7.7%, 100 mg BID: 7.3%, and 200 mg BID: 7.4%), with deepest responses in questions relating to spleen symptoms (satiety, abdominal discomfort, and left rib pain) and cytokine-related symptoms (night sweats, itching, and bone pain), particularly at 200 mg BID. The percentage of patients describing at least minimal improvement of their symptoms based on the Patient Global Impression Assessment (PGIA) at Week 24 was greatest in the 200 mg BID arm (33.3%, n = 18/54) compared with 100 mg BID (23.6%, n = 13/55) or 100 mg QD (19.2%, n = 10/52).

The majority of non-hematologic AEs was mild or moderate in severity, and rates were generally similar across dosing arms with the exception of gastrointestinal events, which occurred more commonly in patients treated at 200 mg BID (39/54, 72.2%) than in patients treated at lower doses (100 mg QD: 26/52, 50.0%; 100 mg BID: 30/55, 54.5%). These events were largely grade 1 or 2 and usually occurred within the first 8 weeks on treatment. Diarrhea was common but generally manageable with standard antidiarrheal agents and tended to be short-lived: the median duration of pacritinib-related diarrhea was 2 weeks. The most common hematologic AEs were thrombocytopenia and anemia, both of which occurred more frequently in patients treated at 200 mg BID (40.7% and 24.1% respectively). Cardiac events were more common in patients treated at 200 mg BID (40.7%, n = 22) than in patients treated at lower doses (100 mg QD: 21.2%, n = 11; 100 mg BID: 21.8%, n = 12) but were largely grade 1 or 2 in severity, with the most common being peripheral edema (200 mg BID: 16.7%) and QT prolongation (200 mg BID: 7.4%). There was no excess in grade 3 or 4 cardiac events in patients treated at the highest dose (100 mg QD: 5.8%, n = 3; 100 mg BID: 5.5%, n = 3; and 200 mg BID: 3.7%, n = 2; no grade 4 events). The mean change in corrected QT interval (QTc) between Baseline and Week 24 was roughly +10 msec on all arms; no patient had a QTc > 500 msec. Bleeding events were more common in patients treated at 200 mg BID (42.6%, n = 23) than in patients treated at lower doses (100 mg QD: 36.5%, n = 19; 100 mg BID: 25.5%, n = 14) but were largely grade 1 or 2 in severity, with the most common being epistaxis (200 mg BID: 14.8%) and bruising (200 mg BID: 9.3%). There was no excess in grade 3 or 4 bleeding events in patients treated at the highest dose (100 mg QD: 7.7%, n = 4; 100 mg BID: 3.6%, n = 2; and 200 mg BID: 5.6%, n = 3; no grade 4 events). The rate of fatal events was similar across all arms: 100 mg QD: 7.7%, n = 4 (sepsis, disease progression, tuberculosis, and general state deterioration); 100 mg BID: 5.5%, n = 3 (myelofibrosis, subdural hemorrhage, and heart failure); and 200 mg BID: 5.6%, n = 3 (sepsis, respiratory failure, and subdural hematoma).

## 2 STUDY RATIONALE AND OBJECTIVES

This study is being conducted to establish the safety and efficacy of pacritinib + standard of care (SOC) compared to placebo + SOC in hospitalized patients with severe COVID-19 with or without cancer as the proportion of patients who progress to IMV and/or ECMO or die by

Day 28. This study will additionally confirm the safety and efficacy of pacritinib administered at 400 mg QD on Day 1 followed by 200 mg BID for up to 14 days, with the option of extending an additional 7 days (for a total of 21 days) with the approval of the Medical Monitor if, in the opinion of the investigator, the patient's clinical signs and symptoms are improving and the potential benefit outweighs the potential risk. Determination of the selected dose is detailed in Section 3.1.

## **2.1 Justification of Included Patient Population**

The study population will consist of hospitalized adult patients with severe COVID-19 with or without cancer. Severe COVID-19 is defined as confirmed disease in patients who are hospitalized with hypoxia [ $\text{SpO}_2 \leq 93\%$  on room air], respiratory rate  $>30$ ,  $\text{PaO}_2/\text{FiO}_2 <300$ , but do not require IMV ([NIH COVID-19 Treatment Guidelines 2020](#)). Patients with moderate COVID-19 are not eligible for the study because it is likely that they will not be receiving supplemental oxygen and will not be hospitalized. Patients with critical COVID-19 are not included because the goal of pacritinib therapy is to prevent patients from progressing to the acute respiratory distress syndrome associated with COVID-19.

## **2.2 Independent Data Monitoring Committee**

This study will be monitored by an Independent Data Monitoring Committee (IDMC). The IDMC will comprise a multidisciplinary group of at least three voting members in the fields of hematology, infectious disease, and biostatistics. Additional personnel may be added to the IDMC at the request of the IDMC membership. The membership, roles, and responsibilities of the IDMC will be fully defined by the IDMC charter.

The IDMC will make independent recommendations to the Sponsor on study continuation (continue without modification, continue with modification, or terminate) and on patient enrollment (hold or stop enrollment or enroll additional patients).

The IDMC charter will be written in collaboration between the Sponsor and members of the IDMC. In keeping with the terms of the charter, each IDMC meeting will have an open and closed session.

The IDMC will convene for a formal safety review after the first 40 patients (approximately 20 patients per arm) have completed treatment and then quarterly thereafter. Subsequent meetings will be triggered at the interim analysis. Ad hoc meetings can be called at any time by either the IDMC or by CTI.

Meeting minutes will be generated from each IDMC meeting and provided to the Food and Drug Administration (FDA) within 10 business days of the meeting conclusion.

## **2.3 Study Objectives**

### **2.3.1 Primary Objective**

To compare the efficacy of pacritinib + standard of care (SOC) versus placebo + SOC in hospitalized patients with severe COVID-19 with or without cancer, as the proportion of patients

who require invasive mechanical ventilation (IMV) and/or extracorporeal membrane oxygenation (ECMO) or die by Day 28.

Severe COVID-19 is defined as confirmed disease in patients who are hospitalized with hypoxia ( $\text{SpO}_2 \leq 93\%$  on room air at sea level), respiratory rate  $>30$ ,  $\text{PaO}_2/\text{FiO}_2 < 300$ , but do not require IMV.

### **2.3.2 *Secondary Objectives***

1. To compare the number of ventilator-free days, defined as the number of days that patients are alive and not intubated, from randomization to Day 28 between pacritinib + SOC versus placebo + SOC
2. To compare the mortality rate between pacritinib + SOC versus placebo + SOC at Day 28
3. To compare the mortality rate between pacritinib + SOC versus placebo + SOC at Day 15
4. To compare the time to improvement by at least 2 points relative to Baseline on the 7-point ordinal scale of clinical status between pacritinib + SOC versus placebo + SOC
5. To compare the clinical status assessed by the 7-point ordinal scale of clinical status at Days 8, 15, 22, and 28 between pacritinib + SOC versus placebo + SOC
6. To compare the rate of use of immunomodulatory agents as treatment for COVID-19 during the 28 days following randomization between pacritinib + SOC versus placebo + SOC
7. To evaluate the toxicity profile of pacritinib therapy in hospitalized patients with severe COVID-19 with or without cancer

### **2.3.3 *Tertiary Objectives***

To evaluate the treatment effects of pacritinib + SOC on the following markers of disease severity:

- C-reactive protein (CRP)
- Ferritin
- D-dimer
- IL-6
- Troponin-I
- Lactate dehydrogenase (LDH)
- Brain natriuretic peptide (BNP)

- Procalcitonin
- Triglycerides
- Creatine kinase (CK)

### **3 STUDY DESIGN**

This is a Phase 2 randomized, double-blind, placebo-controlled, multicenter study to evaluate the efficacy and safety of pacritinib in hospitalized patients with severe COVID-19 with or without cancer. Severe COVID-19 is defined as confirmed disease in patients who are hospitalized with hypoxia ( $\text{SpO}_2 \leq 93\%$  on room air), respiratory rate  $>30$ ,  $\text{PaO}_2/\text{FiO}_2 <300$ , but do not require IMV.

Patients will be randomized 1:1 to receive pacritinib (400 mg QD on Day 1, then 200 mg BID from Day 2 to Day 14) + SOC or placebo + SOC stratified by age (< 60 years versus  $\geq 60$  years) and the 7-point ordinal scale of clinical status scale (baseline 3 or 4 versus 5). The study duration will be 8 weeks.

Assigned treatment will continue for up to Day 14 or until the patient experiences intolerable adverse events (AEs), withdraws consent, or initiates another investigational therapy, or until the study is terminated. Assigned therapy may be given for an additional 7 days (for a total of 21 days) with the approval of the Medical Monitor if, in the opinion of the investigator, the patient's clinical signs and symptoms are improving and the potential benefit outweighs the potential risk. In the event of hospital discharge, patients will complete treatment with the assigned therapy as an outpatient.

The primary endpoint is the effect of treatment on the proportion of patients who require IMV and/or ECMO or die by Day 28.

The study will be monitored by an IDMC comprising a multidisciplinary group of at least three voting members in the fields of hematology, infectious disease, and biostatistics. Additional personnel may be added to the IDMC at the request of the IDMC membership. The membership, roles, and responsibilities of the IDMC will be fully defined by an IDMC charter.

Safety will be monitored with physical examinations, clinical laboratory assessments, and electrocardiogram (ECG) monitoring for inpatients. Patients who are discharged from the hospital while still on study will be monitored weekly. Outpatient monitoring will include telephone/videoconference contact and may also include review of the patient's electronic medical record. Laboratory and ECG assessments will not be required for monitoring outpatients, including those completing their course of study drug. Specified pacritinib/placebo dosage modifications will be followed to address identified abnormalities. AE data will be collected from the time of randomization through 30 days following the last dose of pacritinib/placebo. Serious adverse events (SAEs) assessed as related to pacritinib/placebo or study procedure by the investigator or Sponsor shall be followed until the event resolves, stabilizes or the patient is lost to follow-up. SAEs assessed as unrelated to pacritinib/placebo or study procedures shall be followed for 30 days after the last dose of pacritinib/placebo, or until

the event resolves, returns to baseline, stabilizes, or the patient is lost to follow-up, whichever comes first.

At the request of an investigator, and with agreement of the Chief Medical Officer at CTI, the assigned treatment for an individual patient may be unblinded for the purposes of discussing the ongoing care of that patient.

The approximate study duration for each patient will be 8 weeks. The estimated duration of the entire study is approximately 1 year and is subject to increase as patient enrollment increases.

The schedules of study assessments for all patients are provided in [Table 1](#).

[figure not shown]

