### Study Design

This is a Phase 2 randomized, double-blind, placebo-controlled, multicenter study to evaluate the efficacy and safety of pacritinib in hospitalized patients with severe COVID-19 with or without cancer. Severe COVID-19 is defined as confirmed disease in patients who are hospitalized with hypoxia (blood oxygen saturation [SpO2] ≤93% on room air at sea level), respiratory rate >30, arterial oxygen partial pressure [PaO2]/fraction of inspired oxygen [FiO2] <300, but do not require IMV.

Patients will be randomized 1:1 to receive pacritinib (400 mg once daily [QD] on Day 1, then 200 mg twice daily [BID] from Day 2 to Day 14) + SOC or placebo + SOC.

Assigned treatment will continue for up to Day 14 or until the patient experiences intolerable adverse events (AEs), withdraws consent, or initiates another investigational therapy or until the study is terminated. Assigned therapy may be given for an additional 7 days (for a total of 21 days) with the approval of the Medical Monitor if, in the opinion of the investigator, the patient's clinical signs and symptoms are improving and the potential benefit outweighs the potential risk. In the event of hospital discharge, patients will complete treatment with the assigned therapy as an outpatient.

The primary endpoint is the effect of treatment on the proportion of patients who require IMV and/or ECMO or die by Day 28.

Data analyses will be conducted during the study by an Independent Data Monitoring Committee (IDMC). The membership, roles, and responsibilities of the IDMC will be fully defined by an IDMC charter.

Safety will be monitored with physical examinations, clinical laboratory assessments, and electrocardiogram (ECG) monitoring. Specified pacritinib/placebo dosage modifications will be followed to address identified abnormalities. AE data will be collected from the time of randomization through 30 days following the last dose of pacritinib/placebo. Serious adverse events (SAEs) assessed as related to pacritinib/placebo or study procedure by the investigator or Sponsor shall be followed until the event resolves, stabilizes, or the patient is lost to follow-up. SAEs assessed as unrelated to pacritinib/placebo or study procedures shall be followed for 30 days after the last dose of pacritinib/placebo, or until the event resolves, returns to baseline, stabilizes, or the patient is lost to follow-up, whichever comes first.

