#### **4.1.2     *Exclusion Criteria***

1. In the opinion of the investigator, progression to death is imminent and inevitable within the next 24 hours, irrespective of the provision of treatments
2. Currently intubated or intubated between screening and randomization
3. Suspected active uncontrolled bacterial, fungal, viral, or other infection (besides COVID-19)
4. Prior allogenic hematopoietic stem cell transplantation
5. Active lung cancer or history of lung cancer within the past 12 months
6. Any active grade 2 or higher hemorrhage
7. Any active gastrointestinal or metabolic condition that could interfere with absorption of oral medication
8. Uncontrolled intercurrent illness that, in the judgment of the treating physician, would limit compliance with study requirements
9. Known seropositivity for human immunodeficiency virus with CD4 count < 200/mm^3 within 3 months prior to randomization
10. Pregnant or breastfeeding, or positive pregnancy test in a pre-dose examination
11. Concurrent enrollment in another interventional trial (investigational COVID-19 antiviral studies are permitted)
12. Serum creatinine > 2.5 mg/dL
13. Total bilirubin > 4× the upper limit of normal
14. QT corrected by the Fridericia method (QTcF) prolongation > 480 msec
15. Known history of New York Heart Association Class II, III, or IV congestive heart failure prior to hospital admission
16. Known allergic reaction to any JAK2 inhibitor
17. Exposure to any JAK2 inhibitor within 28 days
18. Currently receiving a strong CYP3A4 inhibitor or strong P450 inducer ([Appendix 1](#) and [Appendix 2](#), respectively) and unable to stop the medication prior to the first dose of study drug and throughout the duration of study drug administration
19. Treatment with cytoreductive chemotherapy administered within 14 days prior to randomization

20. Administration of an IL-1 or IL-6 blocking immunomodulatory agent (such as tocilizumab, canakinumab, sarilumab, anakinra) within 48 hours prior to randomization
21. Currently receiving therapeutic anticoagulation or anti-platelet medication and unable to stop the medication prior to randomization. Prophylactic anticoagulation therapy or aspirin ( $\leq 100$ mg) are permitted.
22. Unable to ingest capsules or tablets at randomization

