## 6.6 Concomitant and Excluded Therapies

Treatment with cytoreductive therapy is not permitted during the assigned treatment period. Pacritinib is metabolized by the P450 system, including cytochrome P450 3A4 (CYP3A4). Use of strong CYP3A4 inhibitors is not permitted as these can lead to significantly increased concentrations of pacritinib. Use of strong cytochrome P450 (CYP450) inducers is not permitted as these can lead to significantly reduced concentrations of pacritinib. Lists of selected strong CYP3A4 inhibitors and P450 inducers are found in [Appendix 1](#) and [Appendix 2](#), respectively.

Concomitant use of investigational agents (those administered as part of a clinical trial) for the treatment of COVID-19 is prohibited with the exception of antiviral agents. The use of IL-1 or IL-6 blocking immunomodulatory agents (such as tocilizumab, canakinumab, sarilumab, anakinra) is allowed if, in the opinion of the investigator, a patient is clinically deteriorating. However, patients who require IL-1 or IL-6 blocking agents must be discontinued from study drug. Hydroxychloroquine, chloroquine, azithromycin, corticosteroids, and antiviral agents are permitted concomitant medications.

Electrolyte repletion should be considered for patients who have electrolyte levels below the lower limit of normal upon entry into the study or while receiving pacritinib/placebo.

Patients who develop worsening gastrointestinal symptoms with the initiation of pacritinib/placebo treatment may be treated with standard antidiarrheal and/or anti-emetic medications (Section [6.6.1](#)).

Treatment-dose anticoagulation and anti-platelet therapy may be administered after randomization, if required; patients do not need to discontinue pacritinib/placebo if one of these medications is initiated. However, patients should not receive such agents concomitant with study drug administration if their platelet counts drop to < 50,000/ $\mu$ L; prophylaxis-dose anticoagulants are permitted for all patients on study. Treatment-dose anticoagulants and anti-platelet agents may be administered at any dose after the study drug treatment period has ended.

Cytotoxic chemotherapy or cancer-directed immunotherapy is prohibited during the pacritinib/placebo treatment period (14 or 21 days). Cancer-directed immunotherapy includes immune checkpoint inhibitors, antibody-based cancer therapy, and cell-based cancer therapy.

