### **3 STUDY OVERVIEW**

#### **3.1 Study Design**

This is a Phase 2 randomized, double-blind, placebo-controlled, multicenter study to evaluate the efficacy and safety of pacritinib in hospitalized patients with severe COVID-19 with or without cancer. Severe COVID-19 is defined as confirmed disease in patients who are hospitalized with hypoxia ( $\text{SpO}_2 \leq 93\%$  on room air), respiratory rate  $>30$ ,  $\text{PaO}_2/\text{FiO}_2 <300$ , or lung infiltrates  $>50\%$  but do not require IMV.

Patients will be randomized 1:1 to receive pacritinib (400 mg QD on Day 1, then 200 mg BID from Day 2 to Day 14) + SOC or placebo + SOC stratified by age (< 60 years versus  $\geq 60$  years) and the 7-point ordinal scale of clinical status scale (baseline 3 or 4 versus 5). The study duration will be 8 weeks.

Assigned treatment will continue for up to Day 14 or until the patient experiences intolerable adverse events (AEs), withdraws consent, or initiates another investigational therapy, or until the study is terminated. Assigned therapy may be given for an additional 7 days (for a total of 21 days) with the approval of the Medical Monitor if, in the opinion of the investigator, the patient's clinical signs and symptoms are improving and the potential benefit outweighs the potential risk. In the event of hospital discharge, patients will complete treatment with the assigned therapy as an outpatient.

The primary endpoint is the effect of treatment on the proportion of patients who require IMV and/or ECMO or die by Day 28.

Ongoing safety monitoring will be conducted by an independent data monitoring committee (IDMC). The IDMC will comprise a multidisciplinary group of at least three voting members in the fields of hematology, infectious disease, and biostatistics. Additional personnel may be

added to the IDMC at the request of the IDMC membership. The membership, roles, and responsibilities of the IDMC will be fully defined by an IDMC charter.

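### The treatment-duration sentence ends study drug when another investigational therapy is started, but Protocol 6.6 exempts investigational antivirals, so two rules apply to the same patient

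*Protocol*

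**What the plan says.** Three places set how long assigned treatment lasts. The Synopsis (Study Design) continues it up to Day 14 or until the patient has intolerable adverse events, "withdraws consent, or initiates another investigational therapy or until the study is terminated". Protocol Section 3 uses the same words: "withdraws consent, or initiates another investigational therapy, or until the study is terminated". SAP 3.1 carries the sentence over: "or initiates another investigational therapy, or until the study is terminated". None of them excepts antivirals.

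Protocol 6.6 (also in the Synopsis) deals with the same agents differently. It explains in parentheses that investigational agents are those given within a clinical trial, and says their use "for the treatment of COVID-19 is prohibited with the exception of antiviral agents". Later in the same paragraph it adds: "Hydroxychloroquine, chloroquine, azithromycin, corticosteroids, and antiviral agents are permitted concomitant medications". Exclusion 11 in Protocol 4.1.2 takes a similar line at entry: "Concurrent enrollment in another interventional trial (investigational COVID-19 antiviral studies are permitted".

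On interactions, the preceding paragraph of 6.6 states: "Use of strong CYP3A4 inhibitors is not permitted as these can lead to significantly increased concentrations of pacritinib". Appendix 1 lists lopinavir and ritonavir among the selected strong inhibitors.

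**The concern.** Study drug is meant to be given for 14 days, or up to 21 with Medical Monitor approval. Whether a patient stays on it should not depend on which page the site consults. A site working from Section 3 would withdraw pacritinib or placebo when a patient starts an antiviral in another trial. A site working from 6.6 would see a permitted co-medication and carry on.

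Stops that arise this way are unrelated to tolerability or effect. They shorten exposure within an intent-to-treat comparison, and they make the recorded discontinuations harder to interpret because some would reflect a reading of the protocol. A smaller issue is that the sentence permitting antivirals carries no qualification, although two drugs on the strong-inhibitor list are antivirals.

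**Working it through.** There is no plan figure to reproduce. The check sets the passages side by side.

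1. **Is an antiviral from another trial an investigational therapy?** Yes. 6.6 defines investigational agents by their being given in a clinical trial. Section 3 therefore cannot easily be read as leaving such an antiviral out.

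2. **What does the duration sentence require?** Starting another investigational therapy ends assigned treatment. The Synopsis, Section 3 and SAP 3.1 agree on this.

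3. **What does 6.6 require?** Investigational agents for COVID-19 are "prohibited with the exception of antiviral agents". Nothing in 6.6 tells the site to stop study drug when an antiviral is used. The contrast within the same paragraph matters: IL-1 and IL-6 blockers are allowed on deterioration, and 6.6 then says explicitly that study drug must be discontinued.

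4. **Does another passage settle it?** Section 6.5.1 names intolerable adverse events, withdrawal of consent to continue and investigator discretion. It does not name starting an investigational therapy. Neither document states which section prevails.

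5. **Apply the rules by case.**
   - *Investigational antiviral started during dosing, not a strong CYP3A4 inhibitor.* Study drug ends under the duration sentence and may continue under 6.6. This is a contradiction.
   - *Patient already in an antiviral trial at entry.* Exclusion 11 allows entry. The duration sentence speaks of initiating a therapy, so it does not clearly apply. There is no clear conflict.
   - *Lopinavir or ritonavir in use at screening.* Exclusion 18 removes the patient only if the drug cannot be stopped before the first dose and kept off during dosing. Exclusions 11 and 18 must both be cleared and do not contradict each other.
   - *Lopinavir or ritonavir started during dosing.* One paragraph of 6.6 does not permit strong inhibitors, and the next permits antivirals without qualification. The specific restriction can be read as limiting the general permission, so this is a missing cross-reference.

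6. **Scale.** The number of patients in the first case is not in the documents. Only a per-patient scale can be given. The sample-size assumptions are 26.5% on placebo and 13.5% on pacritinib, a difference of 26.5 − 13.5 = 13 points. Suppose affected patients would have had the average benefit and lose all of it by stopping. Then each 1% of the pacritinib arm affected reduces the expected difference by 0.01 × 13 = 0.13 percentage point. Partial exposure before stopping would make this smaller. This does not estimate how many patients are affected.

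**The case against.** The best reply is that the duration sentence belongs to design summaries, while 6.6 is the operative section on co-medication. On that view, the words about another investigational therapy simply carry forward the ban in 6.6, which already leaves antivirals out. The silence of 6.5.1 fits that reading. It is a reasonable way to harmonise the text, and many sites might adopt it. But it has to be inferred. The duration sentence is stated as a rule in three places, including the SAP, and no text ranks one section above another.

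Several stronger inferences are tempting, and the other side is right to resist them:

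- A reader might infer that the same patient could be continued, stopped or excluded depending on the page. The case analysis does not bear this out. Exclusion 11 governs entry, the duration sentence governs later initiation, and exclusion 18 bites only when a listed drug cannot be stopped.
- A reader might infer that a site could not apply exclusion 18 to someone in a blinded antiviral trial. That does not follow. A site can check which agents the other trial may assign against Appendix 1, and the appendix directs questions about possible inhibitors to the medical monitor.
- A reader might infer that lopinavir–ritonavir was an expected co-medication because the ordinal scale is adapted from a trial of that combination. The citation supports the scale and says nothing about background care here. The antiviral named in the SAP's Table 8 is remdesivir, which is not in the protocol's Appendix 1.

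**Conclusion.** The point holds in a narrow form. For a patient who starts an investigational antiviral while on study drug, the Synopsis, Section 3 and SAP 3.1 end treatment, and 6.6 allows it to continue. Nothing in either document resolves this. It should be corrected because it decides who stays on blinded treatment. The antiviral and strong-inhibitor wording in 6.6 is a secondary clarification.

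The effect on the trial cannot be sized. The documents report no share of patients expected to co-enrol, to start an investigational antiviral or to be treated at sites reading one rule over the other, so any count of affected patients would be a guess. The per-patient scale in the working suggests that only a sizeable share would move the primary comparison materially, under the assumptions given there.

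A reader might also infer that a stop for this reason would be scored as a primary-endpoint event, because SAP 6.1 counts undischarged patients who discontinue early as having progressed. That section does not say whether it means stopping treatment or leaving the study. However, SAP 6.2.1 uses parallel wording and refers to study discontinuation, and SAP 7.2.1 reports the two separately. The documents therefore do not establish that consequence.

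**What to change.** Reconcile the treatment-duration sentence in the Synopsis, Protocol Section 3 and SAP 3.1 with 6.6, so that all four say the same about an investigational antiviral started during dosing. Which rule applies is a clinical decision for the sponsor's team. Section 6.5.1 should be checked against the chosen wording.

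In 6.6, add a cross-reference so that the sentence permitting antivirals is read together with the restriction on strong CYP3A4 inhibitors and Appendix 1.

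Little new data capture is needed. Concomitant medications are already recorded from consent to 30 days after the last dose (Protocol Table 1, footnote 20), SAP 7.2.4 summarises and lists antivirals separately, and SAP 7.2.1 reports reasons for stopping treatment. A co-enrolment flag would be an optional addition.

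The cost is a clarifying amendment to existing sentences and one matching SAP edit, with no new procedure or visit and no change to the analysis.
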